We estimate a total sample size of 1080 children with SAM (360 per arm) and 1080 children with MAM (360 per arm) will provide at least 90% statistical power to demonstrate non-inferiority for each comparison, with a non-inferiority margin of 10 percentage points, assuming a recovery rate in the control of 77% (Table 4). For relapse outcomes, sample size will be smaller, and thus power will be lower, because only recovered children will be included in the analysis. All calculations assume a one-sided $\alpha = 0.05$ for non-inferiority and two-sided $\alpha = 0.05$ for superiority analyses.

Table 4. Sample size calculations

Scenarios with at least 80% power are **bolded**.

Primary outcome	Analysis type	Sample size per arm	Outcome prevalences reported in literature	Non-inferiority margin or detectable effect size	Assumption on control group outcome prevalence/means in sample size calculations	Power per comparison
Anthropometric recovery at discharge	Non-inferiority	360 MAM and 360 SAM children/arm enrolled; 306 MAM and 306 SAM children in analysis after 15% attrition	MAM recovery (with RUSF*): 73% (13); 73% (14); 85% (15) SAM recovery : 55.4% (16); 82.3% (17); 76% (18); 71% (pooled estimate from meta-analysis) (19)	10 percentage points (absolute difference)	55.4% (vs 45.4%)	85.6%
					77.0% (vs 67.0%)	90.0%
					82.3% (vs 72.3%)	96.8%
Relapse to wasting within 3-months post-discharge	Superiority	236 children/arm in analysis (assuming 77% of the 306 children recover)	Post-MAM relapse : 30% within 3 months (period prevalence) (20); 33% within 12-months (21) Post-SAM relapse : 6.8% 3-month cumulative incidence (22); 24% 2-month cumulative incidence (23); 30% within 3-months (unpublished); 2.6 episodes per child-year (unpublished); 1.3	35% relative reduction (incidence rate ratio = 0.65)	Incidence of 2.6 episodes per child-year	80.0%
					Prevalence of 30% (vs 20%)	71.0%

			episodes per child-year (unpublished)			
--	--	--	--	--	--	--

*RUSF = ready-to-use supplementary food

Study procedures

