All analyses will be delineated in detail in the trial Statistical Analysis Plan (SAP) which will be developed and finalized prior to initiation of enrollment. A summary is given here.

The study is powered for separate comparisons between (i) the control group and SMS-RUTF, and (ii) between the control group and S-RUTF. All analyses will be stratified by MAM vs SAM status.

Baseline characteristics will be assessed with descriptive statistics (means and standard deviations for continuous variables, and proportions for categorical variables). Baseline characteristics will be adjusted for in the analyses if it is both (i) associated with treatment outcomes or relapse in published literature and (ii) imbalanced between treatment arms as determined by statistically significant t-test or χ^2 tests with 5% significance level.

For binary outcomes, we will use log-binomial regression to estimate relative risks (RRs) and 95% confidence intervals (CIs) for the RRs, adjusting for any baseline factors as appropriate. Non-inferiority will be declared if the lower bound of a one-sided 95% CI for the RR lies entirely below the non-inferiority margin of a relative 12.5%. For continuous outcomes, we will use linear regression to estimate differences in that outcome between treatment arms, adjusting for any baseline factors as appropriate. For superiority analyses (relapse), we will use a two-sided 95% CI and superiority will be declared if the lower bound of the 95% CI for the relative risk is above 1.0.

Non-inferiority analyses can be spuriously favored by ITT analyses because non-compliance diminishes any treatment effects, thus biasing the effect size toward the null (35). We will therefore repeat all non-inferiority analyses with a per-protocol (PP) population, restricting the analyses to only children who comply with their full treatment course, per caregiver report. The ITT and PP results will be presented side-by-side for non-inferiority analyses; superiority analyses will be analyzed as ITT only.

Adverse event (AE) and serious adverse event (SAE) monitoring and reporting

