### Sample size and statistical power

#### Main trial

We estimate a total sample size of 1080 children with SAM (360 per arm) and 1080 children with MAM (360 per arm) will provide sufficient statistical power to demonstrate non-inferiority for each comparison, with a non-inferiority margin of relative 12.5%, assuming a recovery rate in the control of 76% and a loss to follow up of 15% (Table 4). The sample size will be smaller for analyses of relapse, because only recovered children will be included in the analysis. All calculations assume a one-sided  $\alpha = 0.05$  for non-inferiority and two-sided  $\alpha = 0.05$  for superiority analyses,  $\beta = 0.8$ , and 15% attrition. While the key objectives of this research are to evaluate effects of the alternative RUTFs on recovery and relapse, we consider as primary outcomes any outcome for which we have adequate power for clinically or policy meaningful effect sizes (5).

 Stata commands `ssi` for continuous outcomes and `artbin` for binary outcomes were used for non-inferiority analyses, and `power twomeans` for continuous outcomes and `power twoproportions` for binary outcomes were used for superiority analyses. Outcome proportions, means, or standard deviations were taken from relevant studies in literature as delineated in Table 4.

Table 4. Calculations of detectable effect sizes for all outcomes

Outcome	Outcome prevalence in the literature	Type of analysis	Non-inferiority margin (relative) with $\geq 80\%$ power (Non-inferiority)	Detectable effect size at 80% power (Superiority)	Rank of outcome
Anthropometric recovery at discharge	MAM recovery (with RUSF*): 73% (6); 73% (7); 85% (8)  SAM recovery: 55.4% (9); 82.3% (10); 76% (11); 71% (pooled estimate from meta-analysis) (12)	Non-inferiority	12.5% relative margin		Primary
Relapse to wasting within 3-months post-discharge	Post-MAM relapse: 30% within 3 months (13); 33% within 12-months (14)  Post-SAM relapse: 6.8% 3-month cumulative incidence (15); 24% 2-month cumulative incidence (16); 30% within 3-months (unpublished)	Superiority		Risk difference of 11%; Relative risk = 0.72	Primary
Length of stay (LOS) among recovered children	MAM: 36.4 days (SD 50.4 days)(17); 5.9 weeks (95% CI: 4.9, 7.0)(18) SAM: 56 days (assumed 41 day SD) (9)	Non-inferiority	MAM: 4.9 days; 12.5% relative margin SAM: 8 days; 12.5% relative margin		Primary

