## Statistical methods

We will conduct two separate comparisons between (i) the control group and SMS-RUTF, and (ii) between the control group and S-RUTF. All analyses will be done separately by wasting severity status (MAM vs SAM); that is, all analyses will be conducted and presented among MAM children and among SAM children separately. No adjustments for multiple comparisons will be made.

For binary outcomes, we will use log-binomial regression to estimate relative risks (RRs) and 95% confidence intervals (CIs) for the RRs, adjusting for any baseline factors as appropriate (described further below). If the regression model is adjusted, we will present both crude (unadjusted) and adjusted model results. If the models do not converge, we will use Poisson regression models with robust estimation of standard errors (26) and report which model was used. Non-inferiority will be declared if the lower bound of a one-sided 95% CI for the RR lies entirely below the non-inferiority margin of a relative 12.5%. For superiority analyses, we will use a two-sided 95% CI and superiority will be declared if the lower bound of the 95% CI for the relative risk is above 1.0. All analyses will be adjusted for health center to reflect the stratified randomization (27–29).

For continuous outcomes measured at one timepoint, we will use linear regression to estimate differences in that outcome between treatment arms, adjusting for any baseline factors as appropriate and health center (as explained above). Both unadjusted and adjusted model results will be presented.

For any outcome for which non-inferiority is demonstrated, we will then sequentially test for superiority. In these cases, we will report both non-inferiority and superiority results. The superiority analysis will be considered exploratory, as the study power calculations were based on non-inferiority effect size.

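### Protocol Table 4 powers recovery on an absolute 10-point margin, but the test to be run uses a relative 12.5% margin; power at 55.4% control recovery is about 58%, not 85.6%

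*Protocol*

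**What the plan says.** The Protocol's Sample size section sets 360 children per arm in each of the MAM and SAM strata, "with a non-inferiority margin of 10 percentage points, assuming a recovery rate in the control of 77" per cent, and claims at least 90% power. Table 4 labels the 10 points as an absolute difference, reduces the analysed number to 306 per arm for 15% attrition, and gives power of 85.6%, 90.0% and 96.8% at control recovery of 55.4%, 77.0% and 82.3%. Alpha is one-sided 0.05.

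The Protocol's Statistical analysis section decides the same outcome on a risk ratio (RR) from log-binomial regression, according to whether the "lower bound of a one-sided 95% CI for the RR lies entirely below the non-inferiority margin of a relative 12.5" per cent.

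The SAP uses the relative margin throughout. Its sample size section works "with a non-inferiority margin of relative 12.5%, assuming a recovery rate in the control of 76% and a loss to follow up of 15" per cent, its Table 4 repeats the 12.5% relative margin for recovery, and its Statistical methods section decides on "the non-inferiority margin of a relative 12.5" per cent. It lists 55.4% among the SAM recovery rates but gives no power by recovery scenario.

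**The concern.** An absolute 10-point margin and a relative 12.5% margin coincide only when control recovery is 80% (0.125 × 80 = 10), which is not a Table 4 scenario. Below 80% the relative margin is the stricter of the two. The Protocol's table is the only place in either document that shows power across recovery rates, so a reader relying on it would take the low-recovery scenario to be comfortably powered.

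That scenario belongs to the sponsor: 55.4% is one of the four SAM recovery rates cited. SAM and MAM are analysed separately, so a shortfall in SAM cannot be made up by MAM.

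**Working it through.** **Inputs.** From the Protocol's Sample size section and Table 4: n = 306 analysed per arm per stratum (360 × 0.85), one-sided alpha 0.05 (z = 1.645), control recovery p = 55.4%, 77.0%, 82.3%. From both decision rules: a relative 12.5% margin, read as RR 0.875, with −ln(0.875) = 0.1335. Assumption, not stated in the documents: true recovery is equal in the arms. Both decision rules are worded with the bound lying below the margin, which is the wrong direction for a favourable outcome. That is a separate point; here success means an RR lower bound above 0.875.

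**1. Reproducing Table 4 on its own 10-point margin.** Power = Φ(0.10/√(2p(1−p)/n) − 1.645). The last column uses a score-test variance.

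| Control recovery | Stated | n = 306 | n = 360 | n = 360, score |
|---|---|---|---|---|
| 55.4% | 85.6% | 80.1% | 85.4% | 85.6% |
| 77.0% | 90.0% | 90.2% | 93.9% | 93.8% |
| 82.3% | 96.8% | 94.5% | 96.9% | 96.8% |

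The middle row matches 306 per arm. The outer rows match 360 per arm, which is the enrolled number before attrition. None of the variants tried at 306 (null variance, score variance, continuity correction, one-sided 0.025, superiority formula) came within 2 points of 85.6% for the first row.

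**2. Power of the test to be run.** Power = Φ(0.1335/√(2(1−p)/(pn)) − 1.645), n = 306.

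- 55.4%: standard error √(2 × 0.446/(0.554 × 306)) = 0.0725; 0.1335/0.0725 = 1.841; Φ(0.196) = 57.8%. A simulation of 400,000 trials gave 58.1%.
- 77.0%: standard error 0.0442; Φ(3.022 − 1.645) = 91.6%.
- 82.3%: standard error 0.0375; Φ(3.562 − 1.645) = 97.2%.
- Other listed rates: 82.6% at 71%, 85.8% at 73%, 90.2% at 76% (the SAP's planning value), 98.9% at 85%.
- Threshold: 79.4% at 69% recovery and 80.2% at 69.5%.

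The relative margin in absolute terms is 0.125 × p: 6.9 points at 55.4%, 9.6 at 77%, 10.3 at 82.3%.

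**3. Splitting the gap at 55.4%.** Stated 85.6% less 57.8% is about 28 points. Correcting the number analysed on the 10-point margin: 85.6% to 80.1%, 5 to 6 points. Changing the margin at 306 per arm: 80.1% to 57.8%, about 22 points.

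**The case against.** The strongest reply is that only one margin ever decides anything. Both analysis sections name the relative 12.5%, and the 10 points appear only in the Protocol's sizing. The SAP already sizes on the relative margin at 76%, where power is 90.2%. This stands: the inconsistency is inside the Protocol, and the SAP's margin is not at fault.

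It is also true that nothing is lost at the planning value: 91.6% at 77% against the stated 90.0%. Converting the margin to 9.6 absolute points would give 88.2%, but the decision is written on the RR. And 55.4% is the lowest of the seven recovery figures listed; the other six, from 71% to 85%, all keep at least 82% on the RR formula.

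The number analysed may exceed 306, because the SAP's missing-data section counts default as an outcome. Even with all 360 analysed, power at 55.4% is only 63.8%.

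Some stronger readings are not supported:

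- A reader might infer that the margin alone turns 85.6% into 58%. It does not; part of the gap is attrition not applied in the table.
- A reader might infer that the trial could return opposite verdicts. The two margins can disagree: 170/306 against 163/306 gives a risk-difference bound of −8.9 points (within 10) and an RR bound of 0.849 (fails 0.875). In simulation they disagreed in 22% of trials at 55.4% and about 1% at 76–77%. But this is hypothetical, since no decision rule uses 10 points. At high recovery it is also fragile: 260 against 245 of 306 passes both (−9.94 points; 0.886).
- A reader might add the SAP's SAM rates for default (8.5%), transfer (20.1%) and non-response (12.5%) to argue that recovery near 59% is likely. SAP Table 1 says non-responders are referred to inpatient care, so the categories can overlap. The rates also come from the same study as the 55.4%, so they are not independent support.

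**Conclusion.** Protocol Table 4's recovery rows are wrong as written. They describe a 10-point test that no analysis section will run, and two of the three rows appear to ignore the 15% attrition stated in the same table. Under the actual rule, power is about 58% / 92% / 97% at 55.4% / 77% / 82.3%, against the stated 85.6% / 90.0% / 96.8%. The only material error is in the low-recovery row; the outer rows' use of 360 per arm is inferred from the match and is not stated.

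This does not show that the trial is underpowered at its planning assumption: the claim of at least 90% power at 77% survives. It shows that power falls below 80% when control recovery is under about 69.5%, which the Protocol's table conceals. The figures rest on equal true recovery, 306 analysed per arm, no covariate adjustment and a normal approximation on the log-RR scale.

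**What to change.** In the Protocol's Sample size section and Table 4, replace the absolute 10-point margin with the relative 12.5% margin already used in the Protocol's Statistical analysis section and in the SAP. Recompute all three recovery rows at 306 per arm under that rule (about 58% / 92% / 97%), and state the equal-recovery assumption. Say plainly that power at 55.4% is about 58% and that 80% power needs control recovery of about 69.5% or more.

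The SAP's margin needs no change. The cost is a wording correction and one recomputed set of table rows. One stated power becomes less favourable; the sample size and the choice of margin in the decision rule stay as they are.

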This will be a facility-based, individually randomized, controlled trial with three arms, including two interventions (SMS-RUTF and S-RUTF) and one control arm (standard RUTF), and a 1:1:1 allocation ratio. Children will be enrolled upon initiation of MAM or SAM treatment and followed for 3 months post-discharge from treatment. The national CMAM protocol of Burkina Faso will be followed when evaluating the different RUTFs.

Randomization procedure

A statistician who is not part of the research team will generate a randomization scheme for the allocation of the 3 supplements. Each unique randomization number is randomly allocated to 1 of 9 letter codes (e.g., A, E, I, Z, K, T, N, E, S)—3 letters for the SMS-RUTF supplement, 3 letters for the S-RUTF supplement and 3 letters for the standard RUTF (control group)—using a computer program in permuted blocks of 15. Without notifying the investigators, the statistician will inform the producers which letters to print on the package of each supplement. Information regarding the assignment of the letter codes to the intervention and control supplements is sealed in opaque envelopes, who locked the envelope away until analysis was completed. Before the study started, the clinical research coordinator will seal each of the randomization numbers with the corresponding letter codes of the RUTF supplements into separate opaque envelopes that were marked with unique participant numbers to be attributed at study inclusion. At study inclusion, the study nurse opens the next sealed envelope in the presence of an eligible mother-child pair (in order of arrival) and provides them with the RUTF supplement according to the letter code. The participant's number, as well as the letter code, will be written down on the study participant's card.

Study participants and determination of eligibility

The population for this study will be children 6-59 months old with MAM or uncomplicated SAM presenting to the study facilities. MAM will be defined as middle upper arm circumference (MUAC) ≥ 11.5 and < 12.5 cm, or weight-for-length/height z-score (WLZ/WHZ) ≥ -3 and < -2 . Uncomplicated SAM (i.e., cases of SAM that are eligible for outpatient treatment) will be defined by all the following criteria: (i) MUAC < 11.5 cm or WLZ/WHZ < -3 , (ii) no clinical complications, and (iii) child passes the appetite test (the child eats at least the amount of RUTF required for passing the appetite test as per Burkina Faso national guidelines (12)).

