- **Alternative, soy-based RUTF (S-RUTF) formulation (intervention 2):** a milk- and peanut-free product with added crystalline amino acids

Burkina Faso national guidelines for MAM and SAM treatment will be followed for dosing the products and all other aspects of treatment (Table 1 and

Table 2). Thus, all children will receive the standard of care for CMAM treatment in Burkina Faso, with the only difference between treatment arms being the product received. Burkina Faso national guidelines for CMAM are detailed in the guideline document (12). Briefly, upon admission to treatment for SAM, children will undergo medical evaluation and receive routine antibiotics and rapid diagnostic test for malaria as well as other treatment as indicated in the guidelines. The caregiver of the child will be provided with RUTF and instructed on how to use it. Children will be followed weekly at the health center to be re-evaluated. At the follow-up visits, children's anthropometry will be measured, a clinical examination will be performed, and the caregiver will be provided with another 7-days' supply of RUTF with instructions. Children will be treated a maximum of 12 weeks and will be eligible to be discharged when they have achieved anthropometric recovery (defined in Table 3). For MAM, upon admission to treatment, children will be provided with RUTF to be used as a food supplement in addition to the child's usual diet. Caregivers will be provided with the product and instructed on its use, and receive nutritional counseling as per guidelines. Children will receive medical treatments as indicated in the guidelines, and instructed to return to the health facility every two weeks for monitoring. Children will be treated for a maximum of 12 weeks and be eligible for discharge when they have achieved anthropometric recovery.

Table 1. Burkina Faso guidelines for dosage for MAM (12)

Sachets per day (92 gram sachets)	Sachets per week (92 gram sachets)	Sachets per two weeks (92 gram sachets)
1	7	14

Table 2. Burkina Faso guidelines for dosage for SAM (12)

Child's weight (kilograms)	RUTF - grams		RUTF – sachets (92 grams)	
	Grams per day	Grams per week	Sachets per day	Sachets per week
3.0-3.4	105	750	1 ¼	8
3.5 – 4.9	130	900	1 ½	10
5.0 – 6.9	200	1400	2	15
7.0 – 9.9	260	1800	3	20
10.0 – 14.9	400	2800	4	30
15.0 – 19.9	450	3200	5	35
20.0 – 29.9*	500	3500	6	40

Storage of product

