All products will be stored according to instructions from the manufacturer, in a dry and cool place at a temperature below 30° C out of direct sunlight. Prior to providing participants with products, the products will be inspected visually for damage. Quality control procedures will be detailed in a study standard operating procedure (SOP).

Outcomes

The outcomes of the study, their definitions, and type of analysis (non-inferiority or superiority) are listed in Table 3. Treatment outcomes will be evaluated through non-inferiority, and post-treatment outcomes will be evaluated through superiority analyses. This is because the intervention products may have the important benefits described above of being lower cost than the standard RUTF, increased potential to be produced locally, and free of aflatoxin, but evidence is needed to confirm they are acceptably similar in treatment outcomes. The composition of these alternative formulations may also improve gut health, possibly reducing the risk of relapse. Thus, post-discharge relapse outcomes are analyzed in superiority analyses.

Table 3. Primary and secondary study outcomes

Outcomes	Definition	Type of analysis
Primary outcomes		
Anthropometric recovery at discharge	WLZ \geq -2 and MUAC \geq 125 mm and absence of bilateral pitting edema for two consecutive visits	Non-inferiority
Relapse to wasting within 3-months post-discharge	A new episode of wasting (defined as WLZ/WHZ $<$ -2 or MUAC $<$ 125 mm or presence of bilateral pitting edema) within the 3-month period following recovery from the index wasting episode, among children who recovered from their index episode	Superiority
Secondary outcomes		
Length of stay (LOS) among recovered children:	The number of days between the day the child is admitted to treatment and the day the child is determined to be recovered and thus discharged from treatment	Non-inferiority
Weight gain	Change in child's weight (gram/kilogram/day) between weight on day of admission to treatment and day of discharge	Non-inferiority
Default from treatment	Child is absent for two consecutive visits, declared a defaulter on the second visit	Non-inferiority
Transfer to inpatient treatment	Referral or admission to hospital for inpatient treatment during the treatment course	Non-inferiority

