All staff will be trained in the study procedures, in order to screen for eligibility, determine eligibility, collect informed consent, administer study products, and conduct follow up procedures in accordance with the trial protocol and SOPs. Before enrollment of the first participant, all study procedures will be piloted for 2 weeks at the study sites to check for any procedural problems, collect feedback from facility staff and communities, and implement any revisions to procedures as needed.

After informed consent is obtained, a unique participant number will be assigned to the participant. Clinical information related to the child's wasting episode, including documentation of routine medications received, child's anthropometry, and clinical status. In addition, the child's medical history and clinical presentation details will be abstracted from their medical records as documented by the study clinician, and copies of the medical records will be stored in the child's study file.

The study nurse will provide counseling on the specifics of wasting treatment as per Burkina Faso guidelines, including the schedule of visits, how to use the RUTF throughout the treatment course, and the duration of treatment. As per Burkina Faso guidelines, the caregiver will return regularly to the facility for follow-up care for their child (weekly for SAM; bi-weekly for MAM), during which they will receive clinical exam to assess morbidity, measurement of anthropometry, and receive another 7-day supply of RUTF. The nurse will answer any questions the caregivers might have. Adherence will be assessed at these follow up visits through caregiver report.

When the child meets the criteria for discharge, children will be counseled to return to the facility for post-discharge follow up monthly for 3 months. At these post-discharge follow-up visits, caregivers will be asked about any admissions to hospital for wasting in the previous month, and the child will be screened for wasting. More details on data collection are given in the following section and in Table 7.

Anthropometric and clinical procedures

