Compliance to treatment services (attendance at visits)	MAM: 87% (17) SAM: 11.1% (11)	Non-inferiority	MAM: 50% relative margin SAM: 10% relative margin		Secondary
Relapse to SAM	Note: Reporting of relapse as MAM vs SAM is not common. Daures et al reported 88.6% of relapses were MAM (23), so we apply this proportion to the below rates.  Post-MAM relapse to SAM: 30% within 3 months (13); 33% within 12-months (14)  Post-SAM relapse to SAM: 6.8% 3-month cumulative incidence (15); 24% 2-month cumulative incidence (16); 30% within 3-months (unpublished)	Superiority		MAM and SAM (Assumed to be same): RR = 0.34	Secondary
Relapse to MAM	Note: Reporting of relapse as MAM vs SAM is not common. Daures et al reported 88.6% of relapses were MAM (23), so we apply this proportion to the below rates.  Post-MAM relapse to SAM: 30% within 3 months (13); 33% within 12-months (14)  Post-SAM relapse to SAM: 6.8% 3-month cumulative incidence (15); 24% 2-month cumulative incidence (16); 30% within 3-months (unpublished)	Superiority	-	MAM and SAM (Assumed to be same): RR = 0.689	Secondary
Morbidity	MAM: 61.1% (any illness) (17) SAM: 60.0% (any illness) (9)	Non-inferiority	MAM: 17.5% relative margin SAM: 17.5% relative margin		Secondary

Anemia at discharge	MAM: 49% prevalence (21) SAM: 51% prevalence (22)	Non-inferiority	MAM: 17.5% relative margin SAM: 17.5% relative margin	--	Secondary
Anemia at 3-months post-discharge	MAM: 49% prevalence (21) SAM: 51% prevalence (22) *estimates are sourced from studies presenting data at discharge because post-discharge data not available	Superiority	--	MAM: 23.3% relative SAM: 24.2% relative	Secondary
Mortality		Non-inferiority			Exploratory

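### Relapse between monthly visits is sought only through a question about hospital admission, so an outpatient-treated episode that clears before the next visit is not counted

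*Protocol*

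**What the plan says.** Protocol Table 3 defines the outcome as a new wasting episode, by WLZ/WHZ below -2, MUAC below 125 mm or edema, "within the 3-month period following recovery from the index wasting episode, among children who recovered from their index episode". SAP Table 1 keeps this definition. It covers the whole period, not only the visit days.

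Under Study procedures, "children will be counseled to return to the facility for post-discharge follow up monthly for 3 months". At those visits "caregivers will be asked about any admissions to hospital for wasting in the previous month, and the child will be screened for wasting". The protocol section on anthropometric and clinical procedures adds monthly measurements and nothing else that bears on relapse.

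On where care is given:

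- Table 3 links hospital to inpatient care in its transfer outcome: "Referral or admission to hospital for inpatient treatment during the treatment course".
- The eligibility section defines uncomplicated SAM as SAM suitable for outpatient treatment. For SAM treatment, "Children will be followed weekly at the health center to be re-evaluated". Children with MAM return to the health facility every two weeks.
- SAP Table 4 notes that a cited cohort "reported 88.6% of relapses were MAM" and applies that proportion to its own relapse rates.

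The SAP adds no rule for ascertaining relapse. Its microbiome sub-study mentions stool collection upon relapse, in a subset of facilities, without saying how the relapse comes to light. The footnote to the SAP accrual figure admits a recovered child to the relapse analysis with one post-discharge visit.

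**The concern.** The recall question should cover the time between visits, but as worded it reaches only inpatient episodes. On the SAP's own figure most relapses are MAM, which is treated at the health center. The protocol also organizes mass screening in surrounding villages and strengthens screening at routine consultations. A relapsed child could therefore be found, re-enrolled as an outpatient and improving before the next study visit.

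Such a child meets the Table 3 definition but is recorded as relapse-free. At stake are the event count of a primary outcome, the power of the relapse comparison, and whether the recorded outcome matches its definition.

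**Working it through.** **Which episodes are missed**

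| Episode after a monthly visit | Visit-day screen | Hospital question |
|---|---|---|
| Still below a cut-off, or edema present, at the next visit | caught | not needed |
| Treated as an inpatient, resolved by the next visit | missed | caught |
| Treated as an outpatient, above both cut-offs without edema at the next visit | missed | missed |

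Only the third row is lost to both methods and recoverable by a better question. An untreated episode that resolves unseen is also lost, but no question about treatment would recover it.

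**How many might be missed**

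Inputs: visit interval L = 365/12 = 30.4 days; mean stay D = 36.4 days for MAM (SD 50.4) and 56 days for SAM (SD 41, assumed in the SAP), both from SAP Table 4. Assumptions: onset uniform over the interval, every episode treated as an outpatient, and stay standing in for time below a cut-off.

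- Fixed length: missed share = max(0, 1 − D/L). Both stays exceed 30.4 days, so the share is 0%.
- Exponential length: missed share = 1 − (D/L)(1 − e^(−L/D)).
  - MAM: 1 − 1.197 × (1 − 0.434) = 0.32.
  - SAM: 1 − 1.842 × (1 − 0.581) = 0.23.

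Stay is not the same as time below a cut-off. Recovery requires the criteria at two consecutive visits, which are two weeks apart for MAM. If the cited 36.4 days included such a confirmation period (an assumption), time below a cut-off would be 36.4 − 14 = 22.4 days, and a fixed length of 22.4 days gives 1 − 22.4/30.4 = 26% missed. Time spent below a cut-off before re-enrollment works the other way and lowers the loss.

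A missed visit doubles the gap to 60.8 days. Even a fixed 36.4-day episode starting in that gap is then missed with probability 1 − 36.4/60.8 = 40%.

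**Effect on power**

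Inputs from Protocol Table 4: 360 × 0.85 × 0.77 = 235.6, taken as n = 236 per arm; 30% vs 20%; two-sided α = 0.05. SAP Table 4 gives a detectable effect but does not state the control rate used, so the protocol's row is the one to work from.

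Power = Φ{[d − 1.96 √(2p̄(1−p̄)/n)] / √[(p1(1−p1) + p2(1−p2))/n]}, where d = p1 − p2 and p̄ is the mean of p1 and p2.

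The plan's own figure: [0.10 − 1.96 × 0.03986] / 0.03960 = 0.552, and Φ(0.552) = 71.0%, which matches the protocol.

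Next, multiply both proportions by a capture fraction s, equal in both arms, with no false positives. The values of s are assumed.

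| s | Recorded relapse | Power | n per arm for 80% |
|---|---|---|---|
| 1.00 | 30% vs 20% | 71.0% | 294 |
| 0.95 | 28.5% vs 19% | 68.0% | 314 |
| 0.90 | 27% vs 18% | 64.9% | 337 |
| 0.80 | 24% vs 16% | 58.5% | 392 |
| 0.70 | 21% vs 14% | 51.7% | 462 |

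The relative risk stays at 0.67 in every row.

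**The case against.** The visit-day screen is the main detector. Weight, length and MUAC are measured twice, and any one of WLZ/WHZ, MUAC or edema is enough for relapse. To be missed, an episode must start, be treated and clear every criterion within about 30 days, while both stays the SAP cites are longer than that. This stands, and it is why the loss may be close to zero.

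The wording may also be looser than it looks. The Costing section speaks of study hospitals in a trial run in health centers, so hospital could have been meant broadly. The SOPs and questionnaires are not shown, the cell markings of Protocol Table 7 did not survive extraction, and SAP Table 6 records admission type, including readmission and relapse, at enrollment. These are reasons to ask the sponsor what was done. They do not close the gap, because neither document says that outpatient re-enrollment is asked about after discharge or counts as relapse.

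The 30% may itself be an observed rate. If the source studies also relied on periodic visits, scaling it down counts the loss twice. That stands as a limit on the power figures.

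A reader might infer that the gap biases the comparison between arms. The documents do not support that. The response that matters here is to re-treatment after relapse, and no passage says a relapsed child receives the allocated product again. Nor does any passage suggest that care-seeking differs by arm.

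**Conclusion.** The point holds as a gap in ascertaining a primary outcome. Between visits, the stated procedure reaches inpatient episodes only, and outpatient episodes that clear before the next visit go uncounted. The share lost is not in the documents and ranges from near 0 to about one third under the duration assumptions shown with all visits attended; missed visits widen the gap.

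With equal capture in all arms and no false positives, the relative risk is unaffected. Power falls from 71.0% to about 65% with 10% missed, or 58% with 20%, taking 30% as the true rate. That scenario was already below 80%.

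Two stronger readings should be resisted. One is that outpatient-treated relapses are generally missed: any episode still present on a visit day is caught. The other is bias by arm, which needs capture to differ by arm. With equal true relapse, capture of 90% in control and 80% in intervention would give a relative risk of 0.80/0.90 = 0.89, and the reverse 1.13, but nothing in the documents shows such a difference.

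**What to change.** - At each post-discharge visit, ask about any re-enrollment in MAM or SAM treatment, outpatient or inpatient, since the last visit, and check the child's health-center card or the study facility's register.
- State in the SAP that a re-enrollment whose recorded anthropometry or edema meets the Table 3 definition counts as relapse, dated at re-enrollment.
- If follow-up is already complete, abstract the study facilities' registers blind to arm where feasible, and report relapse with and without the added episodes. The SAP describes late-enrollment events in the past tense, so this may be the relevant case.

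During follow-up the cost is one reworded question and a card or register check. Retrospective abstraction is more work: it may span 30 facilities, and the record abstraction described in the protocol concerns the enrollment episode, so this would be an addition. Care sought outside the study facilities would still rest on caregiver report, and could not be recovered from the registers afterwards.
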